### ***Risk mitigation***

In the forthcoming study patient risk will be minimized by implementing conservative eligibility criteria. Subjects with increased risk for GI perforations and lymphoproliferative disorders are excluded from the study. Any potential negative effects of GLPG0634 on hematological, clinical chemistry and hormonal parameters will be carefully assessed through regular physical assessments and laboratory monitoring that will happen at each and every visit. Individual stopping criteria have been generated by Galapagos and these provide guidance to the investigators throughout the study. Subjects will also be strictly monitored for occurrence of infections in the course of the study, while subjects at risk of severe infections (including subjects who have recently required parenteral antibiotics or recent infection with herpes zoster), tuberculosis, human immunodeficiency virus (HIV) positive subjects or hepatitis B or C subjects are excluded from enrolment. Special attention to the male reproductive system is applied throughout the study with hormones (testosterone, FSH, LH, PRL and inhibin B) being carefully monitored. An independent Data Safety Monitoring Board (DSMB) will regularly review safety data.

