### 8.3.4 Removal of Subjects from Therapy or Assessments

Subjects may stop study medication for any of the following reasons:

- Subject request.
- Use of nonpermitted concurrent therapy.
- Noncompliance with the study medication (see Section 8.5.9).
- Noncompliance with the study procedures (see Section 8.5.9 and Section 8.6).
- Lost to follow-up.
- Occurrence of AEs not compatible with the continuation of subject participation in the study, in the investigator's opinion. This also includes any clinically significant laboratory results, ECGs, and vital signs.
- Investigator request.
- Sponsor request.
- Treatment failure deemed by the investigator as lack of improvement or worsening of the disease symptoms or occurrence of intolerable AEs.

Treatment with GLPG0634 will be discontinued and the patient withdrawn from this study for:

- Serious infections (those requiring parenteral antimicrobial therapy or hospitalization).
- Any opportunistic infections.
- Complicated herpes zoster infection (multi-dermatomal, disseminated, ophthalmic or CNS involvement).
- Two sequential total white cell counts  $<2000$  cells/mm^3 (SI:  $<2.0 \times 10^9$  cells/L).
- Two sequential neutrophil counts  $<1000$  neutrophils/mm^3 (SI:  $<1.0 \times 10^9$  cells/L).
- Two sequential lymphocyte counts  $<750$  lymphocytes/mm^3 (SI:  $<0.75 \times 10^9$  cells/L).
- Two sequential hemoglobin  $<8.0$  g/dL (SI:  $<80$  g/L).
- Two sequential platelet counts  $<75,000$  platelets/mm^3 (SI:  $<75.0 \times 10^9$  cells/L).
- Two sequential AST or ALT elevations  $>3$  times the upper limit of normal with at least one total Bilirubin value  $>2$  times the upper limit of normal.
- Two sequential AST or ALT elevations  $>3$  times the upper limit of normal accompanied by symptoms consistent with hepatic injury.
- Two sequential AST or ALT elevations  $>3$  times the upper limit of normal accompanied by elevated INR.
- Two sequential AST or ALT elevations  $>5$  times the upper limit of normal, regardless of total Bilirubin or accompanying symptoms.
- Two sequential increases in serum creatinine  $>50\%$  over the average of screening and baseline values.
- Two sequential decreases from the baseline of inhibin B by 50% or Testosterone by 50% with concurrent increases in FSH or LH respectively.

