### **8.5.6 Selection and Timing of Dose for Each Subject**

The study medication will be administered daily with a glass of water in the morning.

Each subject's dose will be selected by random allocation according to randomization procedures.

If a subject misses a dose (e.g., because he/she forgot to take the medication), he/she should take the missed dose within 5 hours after the planned intake time. If the study medication is not taken within 5 hours after the planned time, the missed dose should be skipped. For each dose taken, the number of capsules taken should be recorded on the subject's diary card. Additional to the number of capsules taken, the date and time of the very first intake, and for selected visits, the 2 most recent intakes prior to the visits will be recorded on the subject's diary card. During each visit, the investigator will record a summary of the study medication intake data in the eCRF.

Dose reduction during the study is not allowed. Instead, the subject should either temporarily stop all intake or permanently stop study medication. Every effort should be made to contact the medical monitor before stopping study medication (temporarily or permanently).

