**8.7.1.4.2 Clinical Laboratory Evaluation**

The hematology, clinical chemistry, and urinalysis laboratory analyses will be performed at a central laboratory ([REDACTED]). Reference ranges will be supplied by the central laboratory and used by the investigator to assess the laboratory data for clinical significance and pathological changes.

The total amount of blood to be taken during the study will not exceed 600 mL.

The following laboratory safety tests will be performed at every visit:

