### **Hormone tests (for male subjects only)**

Testosterone (total and free), LH, FSH, prolactin, and inhibin B.

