**8.7.1.5 Flow Chart**

Event	Screening	Baseline 	Treatment period 									FU visit 
			D8/ W1	D15/ W2	D29/ W4	D57/ W8	D85/ W12	D113/ W16	D141/ W20	D169/ W24	EDV 	
Informed consent	Written informed consent will be obtained before any study-related procedures and/or assessments are performed.											
Inclusion/ exclusion criteria	X	X 										
Demographic data and baseline disease characteristics	X											
Medical history/ concomitant illnesses	X											
Physical examination	X 	X					X			X	X	X
Serology 	X											
TB test and chest X-ray 	X											
Pregnancy test 	X	X	X	X	X	X	X	X	X	X	X	X
12-Lead ECG	X						X			X	X	X
Vital signs 	X	X	X	X	X	X	X	X	X	X	X	X
Clinical laboratory tests 	X	X	X	X	X	X	X	X	X	X	X	X
PK samples  blood					X		X			X	X	
PD samples  blood		X	X		X		X			X	X	

 Subjects will begin to take their treatment on the next morning (Day 1) following randomization.

 During the treatment period, a visit time window of  $\pm 2$  calendar days is allowed.

 Follow-up visit will be performed only for subjects discontinuing prematurely from the study and for subjects not entering the Long Term Follow-up study GLPG0634-CL-205.

 Early discontinuation visit.

 Eligibility criteria check based on the laboratory results from the Screening visit.

 At Screening, includes height and weight.

 Includes Hepatitis B and C, HIV 1 and 2, RF, and anti-CCP.

 X-ray should be performed if results from an X-ray performed in the previous 3 months are not available at the site.

 For female subjects only. To be performed on serum at Screening and Week 24/EDV and on urine for other visits.

 Vital signs are defined as blood pressure (systolic and diastolic), HR, and oral temperature.

 Refer to Section 8.7.1.4.2.

 PK samples: 1 blood sample (2 mL) for analysis of GLPG0634 and its main metabolite (G254445) in plasma.

 PD samples: 4 blood samples (2x4 mL for serum preparation and 2x2.5 mL in PAXgene tubes) will be collected for analysis of serum (analytes and miRNA profiling) and whole blood (gene expression in circulating leukocytes, mRNA and miRNA profiling).

CONFIDENTIAL

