6.3.2. Changes after Interim Database Lock but before Final Database Lock

Changes from 1.0 to 2.0 SAP:

Corrections:

- The analysis periods were updated from the interim SAP: the actual Week 12 visit date day is now included in the first 12 weeks of the study period. In the interim SAP it was mistakenly excluded from the first 12 weeks of the study.
- Randomization stratification factors: it is now more clearly specified that in case of discrepancies between IWRS and eCRF, the real underlying eCRF stratum will be used in the analyses and analysis models. This was already so in the interim analysis, but possibly not clear enough in this SAP.
- For safety data, the overall total was replaced by a total across the GLPG0634 groups only. This will allow easier comparison of the overall GLPG0634 safety versus the placebo group.
- Baseline HAQ-DI, Baseline SDAI and Baseline CDAI will be added in the table on baseline disease characteristics.
- VAS plots on percent changes from baseline: from the interim analysis it seemed that the mean values were not so much influenced by the few outliers as initially anticipated. Therefore medians are no longer needed: plots will be mean plots just like all other efficacy parameters.
- Scatterplots between PK plasma levels and safety (lab safety and ECG QTcF) were removed. Because PK plasma sampling can happen at any time relative to the last drug intake ('sparse sampling'), the result is not always representing the subject's exposure. Making a correlation between the PK finding and safety would then be misleading.

Additions:

- Pharmacodynamic analyses were added and specified for the final analysis.
- DAS28(CRP) remission and low disease activity, CDAI remission, SDAI remission: between-group inferential statistics were added, similar to the ACR20 analysis, to allow a more detailed interpretation of the results.

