Frequency table (with cumulative percentages) per lab test category (hematology, biochemistry, endocrine, urinalysis), lab test, treatment group and time point.

Table for selected tests only.

Population: safety.

Table to be created for the Week 12 interim analysis as well.

Table 14.3.2.10: Laboratory data up to Week 12: Shift table of the ATP III classes per time point

Shift table per lab test category (hematology, biochemistry, endocrine, urinalysis), lab test, treatment group and time point. The table will present the shift in ATP III class at worst-case and last on-treatment (other time points: not needed) versus the baseline class.

Table for selected tests only.

Population: safety.

Table 14.3.2.11: Laboratory data up to Week 12: Treatment-emergent ATP III classes per time point

Frequency table of the treatment-emergent lab ATP III classes per lab test category (hematology, biochemistry), lab test, treatment group and time point (including worst-case). A post-baseline class is considered treatment-emergent if it differs from the baseline result and is of higher category.

Table for selected tests only.

Population: safety.

Table to be created for the Week 12 interim analysis as well.

Table 14.3.2.12: Laboratory data up to Week 12: Frequency table of percent changes from baseline per time point in inhibin B and testosterone

Frequency table of the percent changes from baseline per lab test category (endocrine), lab test, treatment group and time point. The percent changes from baseline will be categorized

as: <-50%, [-50%,+50%], >+50%. A worst-case will also be shown selected as the lowest post-baseline value.

Table only for inhibin B, free testosterone, total testosterone.

Population: safety – males.

Population: safety, selecting male subjects with a baseline value within normal range.

Table to be created for the Week 12 interim analysis as well.

Table 14.3.2.13: Laboratory data up to Week 12: Shift table of the categorical lab data per time point

Shift table per lab test category (hematology, biochemistry, endocrine, urinalysis), lab test, treatment group and time point. Selecting only the tests with categorical data. The table will present the shift in value at each post-baseline time point versus the baseline value.

Population: safety.

12.2.10. Figures up to Week 12

Figure 14.3.2.1: Laboratory data up to Week 12: Mean plots of the actual values over time

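### No clock window is set for male hormone draws, and Table 14.3.2.12 compares the lowest single value with one pre-dose sample, so part of its count below -50% may be time-of-day and sampling variation

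*Protocol*

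**What the plan says.** **Collection.** Protocol 8.7.1.4.2 states "The following laboratory safety tests will be performed at every visit" and lists for men "Testosterone (total and free), LH, FSH, prolactin, and inhibin B". The flow chart in 8.7.1.5 places clinical laboratory tests at Screening, Baseline and each later visit. Its footnote reads "During the treatment period, a visit time window of" ±2 calendar days and names no hour. The one morning rule concerns dosing (8.5.6): "The study medication will be administered daily with a glass of water in the morning".

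**Analysis.** SAP 12.2.4 takes as baseline the last sample before first dose, test by test. Table 14.3.2.12 (SAP 12.2.9) puts percent changes in inhibin B and in free and total testosterone into three classes, the lowest being a fall of more than 50%. It adds: "A worst-case will also be shown selected as the lowest post-baseline value". It asks for no second value. The table is also produced for the Week 12 interim and is repeated over 24 weeks as Table 14.3.2.25.

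**Withdrawal criterion.** Protocol 8.3.4 uses a stricter rule: "Two sequential decreases from the baseline of inhibin B by 50% or Testosterone by 50% with concurrent increases in FSH or LH respectively". A retest follows within 3 to 5 days. In the same list, creatinine is judged against the mean of the screening and baseline values.

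**Importance.** Protocol 6.5, under risk mitigation: "Special attention to the male reproductive system is applied throughout the study".

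**The concern.** A percent change from one sample carries the error of that sample into every later comparison. Taking the minimum over several visits then selects the most extreme error. If testosterone also varies over the day, a free choice of appointment time adds a further component to both the baseline and the follow-up values. Neither component says anything about the drug.

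The table is the main categorical display of a safety topic that the protocol singles out. Only the men in each arm contribute, and their number is not stated, so a few chance cases can blur a dose pattern. The interim version of the table is available when preliminary phase III doses are chosen (Protocol 8.8.1.5). In the 24-week version, SAP 2.1.2 shows the former placebo group as switched to 100 mg, so after Week 12 there is no concurrent placebo group to show how many falls occur by chance.

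The SAP accepts a related argument. Section 6.3.2 removed the scatterplots of plasma level against safety because "PK plasma sampling can happen at any time relative to the last drug intake". That sentence concerns PK samples, so it is only indirect evidence that draw times vary at visits.

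**Working it through.** The plan states no figure for this point, so there is none to reproduce.

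**Inputs from the documents**
- One pre-dose reference sample (SAP 12.2.4).
- Five scheduled post-baseline samples to Week 12 (Weeks 1, 2, 4, 8, 12), and eight to Week 24 (adding 16, 20, 24).
- Cut at -50%; lowest value taken; no confirmation (Table 14.3.2.12).

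**Assumptions, not in the documents**
- Daily swing d: log testosterone falls linearly over the clinic day to (1-d) times its start; d = 0, 20, 30, 40%. The existence of a swing, as well as its size, is an assumption.
- Other within-man variation is lognormal with CV 10 to 25%.
- Visit times are uniform over the clinic day; there is no drug effect.

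**Step 1: can the swing alone reach the cut?** The further fall needed after a drop d is 1 - 0.5/(1-d).
- d = 20%: 1 - 0.5/0.8 = 37.5%
- d = 30%: 1 - 0.5/0.7 = 28.6%
- d = 40%: 1 - 0.5/0.6 = 16.7%

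So it cannot over this range; other variation must supply the rest.

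**Step 2: share of men with a worst case below -50%** (simulation, 200,000 men per setting, 8 samples, one shared baseline)

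| CV | d = 0 | 20% | 30% | 40% |
|---|---|---|---|---|
| 10% | 0.0% | 0.01% | 0.1% | 1.0% |
| 15% | 0.4% | 0.9% | 2.0% | 5.0% |
| 20% | 3.9% | 5.4% | 7.6% | 11.8% |
| 25% | 11.7% | 13.4% | 15.7% | 19.8% |

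With the 5 samples to Week 12 and CV 20%, swings of 20%, 30% and 40% give 3.7%, 5.3% and 8.6%.

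The d = 0 column is what the single baseline and lowest-value rule produce without any clock effect. The clock effect is the difference along a row. At CV 20% it is 1.5 to 7.9 points, so swings of 30% and 40% multiply the background by about 1.9 (7.6/3.9) and 3.0 (11.8/3.9). At CV 25% it is 1.7 to 8.1 points on a background that is already 11.7%.

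**Step 3: the adverse ordering.** For one visit with baseline at the daily peak and follow-up at the trough, P = Φ((ln 0.5 - ln(1-d))/s), where s = √(2 ln(1+CV²)). At CV 20%, s = √(2 × 0.0392) = 0.280. For d = 40%, (−0.693 + 0.511)/0.280 = −0.65, which gives 25.8%. For d = 20% and 30% it gives 4.7% and 11.5%. These are conditional figures for one unfavourable order; the reverse order hides true falls.

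**Step 4: the withdrawal criterion.** At CV 20%, 8 samples and d = 20, 30, 40%, a low value confirmed on a retest at a random time occurs in 0.7%, 1.2% and 2.2% of men. Also requiring LH above baseline on both samples (LH taken as independent noise) gives 0.25%, 0.4% and 0.9%.

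**Step 5: effect of the fix.** At a fixed clock time, using the mean of two pre-dose samples lowers the worst-case share from 3.9% to 1.7% at CV 20%, and from 11.7% to 8.0% at CV 25%. Adding confirmation brings these to 0.06% and 0.63%.

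**The case against.** **The size rests on outside inputs.** Neither the swing nor the CV is in the documents. This stands: the figures are conditional, and at CV 10% the effect is negligible. The design features that produce it are in the documents, however, and at CV 20% or more the table counts chance falls even with no swing at all.

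**Collection details may be elsewhere.** Samples go to a central laboratory, and SAP 12.2.13 lists a fasted flag although the protocol sets no fasting rule for these draws. A laboratory manual could therefore fix the hour. That cannot be checked here. The documents are silent on clock time; they do not say that any time is acceptable.

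**The consequence is limited.** The table is descriptive and carries no p-values. Mean changes for endocrine tests are tabulated separately, and placebo is concurrent to Week 12. All of this stands and lowers the weight of the point. It does not help after Week 12.

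**Stronger readings do not hold.** A reader might infer that time of day by itself produces a 50% fall; Step 1 shows that it does not for swings up to 40%. A reader might apply the peak-to-trough figures to all visits, or multiply them by eight; they describe one ordering, and the eight comparisons share one baseline, so they are correlated. A reader might also treat the withdrawal criterion as equally exposed; the second fall and the LH rise largely protect it.

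**Filtering could hide a true low value.** Dropping out-of-window values from the main table would conflict with SAP 4.6, which keeps all measured values, and with SAP 12.2.8, which keeps unscheduled and unselected values in the worst case. This stands, and it is why the in-window version should be additional.

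**Conclusion.** The point holds as a limited design weakness in a safety display. With no drug effect, random clinic times, 8 samples and CV 20%, 3.9% of men would show a worst case below -50% at a fixed clock time, and 5.4% to 11.8% with an assumed swing of 20% to 40%. The corresponding figures are 0.4% against 0.9-5.0% at CV 15%, and 11.7% against 13.4-19.8% at CV 25%. Clock time is thus one part of the excess. The single reference sample and the unconfirmed minimum are the other part, and at CV 25% they are the larger part.

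To Week 12 randomisation should spread this noise evenly, so it raises the background and makes a dose pattern harder to see without favouring any arm. In the 24-week table there is no placebo group after Week 12 against which to judge it. The documents do not support a claim that subjects would often be withdrawn for this reason: under the same assumptions at CV 20% the chance is below 1%. It is not zero, because the LH rise has no stated size and the retest no stated hour.

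**What to change.** **Protocol 8.7.1.4.2.** Require scheduled male hormone samples (Screening, Baseline and each visit) to be drawn in one consistent clock window, and record the draw time.

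**SAP 12.2.9 and 12.2.11.** Leave Tables 14.3.2.12 and 14.3.2.25 as they are, with all values. Add one supportive version that uses in-window samples, counts a fall only if a second value confirms it, and takes the mean of the screening and baseline values as reference. Both pre-dose samples are already scheduled, so no extra blood is needed.

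**Cost.** Timed appointments for male subjects, one recorded field and one extra table. No change to the withdrawal criterion or its retest is proposed.

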### **Urinalysis**

pH, glucose, ketone bodies, indicators of blood and WBC, and protein (quantitative).

Urine pregnancy test for females of childbearing potential at all visits, excluding Screening and Week 24 or EDV.

#### **8.7.1.4.3 Other Laboratory Variables**

##### **Serology**

Hepatitis B and C, HIV 1 and 2, RF and anti-CCP at Screening only.

##### **Other**

TB (QuantIFERON-TB Gold) test at Screening only.

#### **8.7.1.4.4 Vital Signs**

Vital signs (blood pressure, HR and oral temperature) will be recorded as described in the schedule of observations in a standardized manner, i.e., after the subject has rested in the sitting position for 5 minutes.

#### **8.7.1.4.5 Physical Examination**

A physical examination will be performed at times as described in the schedule of observations. Any changes from the Baseline assessment will be recorded. Height and weight will be measured at Screening only.

#### **8.7.1.4.6 Other Safety Assessments**

##### **12-lead Electrocardiogram**

A resting 12-lead ECG will be performed at times presented in the schedule of observations.

Subjects should rest for at least 5 minutes in the supine position before ECG evaluation.

Parameters to be recorded in the eCRF include: HR, RR, QRS, uncorrected QT interval, morphology, and rhythm analysis. QT interval corrected by Friderica's formula will be derived during the statistical analysis. ECGs will be interpreted by the investigator for clinical significance and results will be entered into the eCRF.

##### **Chest X-ray**

A chest X-ray (both anterior-posterior and lateral views) will be taken during the Screening period and reviewed by a qualified radiologist. If chest radiographs have been taken within 3 months of the Screening visit (documented evidence is needed) then the chest radiographs do not need to be repeated (as long as they demonstrate no clinically significant abnormality, and no signs or symptoms suggestive of lung disease including current active or latent TB, which would exclude the subject from the study). The results must be entered into the eCRF.

**8.7.1.5 Flow Chart**

Event	Screening	Baseline 	Treatment period 									FU visit 
			D8/ W1	D15/ W2	D29/ W4	D57/ W8	D85/ W12	D113/ W16	D141/ W20	D169/ W24	EDV 	
Informed consent	Written informed consent will be obtained before any study-related procedures and/or assessments are performed.											
Inclusion/ exclusion criteria	X	X 										
Demographic data and baseline disease characteristics	X											
Medical history/ concomitant illnesses	X											
Physical examination	X 	X					X			X	X	X
Serology 	X											
TB test and chest X-ray 	X											
Pregnancy test 	X	X	X	X	X	X	X	X	X	X	X	X
12-Lead ECG	X						X			X	X	X
Vital signs 	X	X	X	X	X	X	X	X	X	X	X	X
Clinical laboratory tests 	X	X	X	X	X	X	X	X	X	X	X	X
PK samples  blood					X		X			X	X	
PD samples  blood		X	X		X		X			X	X	

 Subjects will begin to take their treatment on the next morning (Day 1) following randomization.

 During the treatment period, a visit time window of  $\pm 2$  calendar days is allowed.

 Follow-up visit will be performed only for subjects discontinuing prematurely from the study and for subjects not entering the Long Term Follow-up study GLPG0634-CL-205.

 Early discontinuation visit.

 Eligibility criteria check based on the laboratory results from the Screening visit.

 At Screening, includes height and weight.

 Includes Hepatitis B and C, HIV 1 and 2, RF, and anti-CCP.

 X-ray should be performed if results from an X-ray performed in the previous 3 months are not available at the site.

 For female subjects only. To be performed on serum at Screening and Week 24/EDV and on urine for other visits.

 Vital signs are defined as blood pressure (systolic and diastolic), HR, and oral temperature.

 Refer to Section 8.7.1.4.2.

 PK samples: 1 blood sample (2 mL) for analysis of GLPG0634 and its main metabolite (G254445) in plasma.

 PD samples: 4 blood samples (2x4 mL for serum preparation and 2x2.5 mL in PAXgene tubes) will be collected for analysis of serum (analytes and miRNA profiling) and whole blood (gene expression in circulating leukocytes, mRNA and miRNA profiling).

CONFIDENTIAL

Event	Screening	Baseline 	Treatment period 									FU visit 
			D8/ W1	D15/ W2	D29/ W4	D57/ W8	D85/ W12	D113/ W16	D141/ W20	D169/ W24	EDV 	
Randomization		X 					X 					
IXRS call	X	X	X	X	X	X	X	X	X	X	X	
Dispense study medication		X	X	X	X	X	X	X	X			
Subject diary card dispensation 		X	X	X	X	X	X	X	X			
Subject diary card collection			X	X	X	X	X	X	X	X	X	
Drug accountability check			X	X	X	X	X	X	X	X	X	
Study medication dosing			▶									
Serum CRP	X	X	X	X	X	X	X	X	X	X	X	
SJC66	X	X	X	X	X	X	X	X	X	X	X	
TJC68	X	X	X	X	X	X	X	X	X	X	X	
Physician's Global Assessment		X	X	X	X	X	X	X	X	X	X	
Patient's Global Assessment	X	X	X	X	X	X	X	X	X	X	X	
HAQ-DI		X	X	X	X	X	X	X	X	X	X	
FACIT fatigue scale		X			X		X			X	X	
SF-36 questionnaire		X			X		X			X	X	
AE assessment	▶											
Concomitant medications	▶											

 Subjects will begin to take their treatment on the next morning (Day 1) following randomization.  
 During the treatment period, a visit time window of ± 2 calendar days is allowed.  
 Follow-up visit will be performed only for subjects discontinuing prematurely from the study and for subjects not entering the Long Term Follow-up study GLPG0634-CL-205.  
 Early discontinuation visit.  
 Upon qualification for the study.  
 At Week 12, all subjects on placebo and the subjects on the 50 mg dose who have not achieved a 20% improvement in SJC66 and TJC68 will be assigned (automatically via IXRS) to 100 mg q.d. in a blinded fashion and will continue in the study until Week 24.  
 Subject diary card will be dispensed to subjects on D -1 and at every following visit; subjects should be instructed to bring their diary card along with them to all visits.

